Statistical analysis plan

Title (preliminary):

“Impact of multifactorial lifestyle interventions on psychosocial well-being for children living with obesity.”

Suggested authors:

[name]*,

[name]*,

[name]

[name]

[name]

[name]

*shared first co-authorship / these authors will contribute equally to the preformed work

Purpose:

To provide an overview of the study design, context, and objectives, as well as to describe how the data management and data analyses will be performed. The statistical analysis plan will be attached as a supplementary document upon submission.

Introduction:

The continuous rise in overweight and obesity among children has become a critical public health issue, due to the associated risks of continuous obesity and development of metabolic disorders in adulthood (1-4).

While these consequences may not be apparent until later in life, the obesity-related complications typically seen in childhood are related to attenuated psychosocial well-being (5). Childhood obesity has been shown associated with reduced self-image, poor self-esteem, bullying and stigmatization (2, 3). Furthermore, children and adolescents with obesity have a higher risk of impaired health-related quality of life (QoL) compared with children not characterized as obese (6-8). QoL in children with obesity has shown to be inversely related to the degree of obesity and the physical, social, and school functioning is significantly lower for children with obesity (8-10). In addition, children with obesity have been reported more likely to suffer from depression and anxiety (11-13). Therefore, there is consensus that increasing levels of obesity is a potential risk factor for reduced psychosocial well-being in children and adolescents (14).

While there is agreement that obesity is associated with reduced psychosocial well-being in children and adolescents, studies evaluating how a lifestyle intervention affects psychosocial well-being remain

scarce. Hence, little is known about the long-term impact of obesity treatment on the psychosocial well-being in children with obesity (15).

Considering the high prevalence of impaired well-being in children with obesity, it is necessary to identify effective lifestyle interventions that can handle and improve this issue (16-18).

Objective:

To investigate the long-term changes in psychosocial well-being in children living with obesity after participation in one of two multifactorial family-centered lifestyle interventions. Furthermore, to compare this alteration in psychosocial well-being between the intervention groups and with a reference group of children who were never invited to participate in the interventions. Also, we aim to investigate the effect that is not caused by the weight change by adjusting for this.

Methods:

Design:

This observational cohort study includes children living with obesity in two municipalities in Denmark between August 1st, 2014, and June 30th, 2020. The children were followed until February 1st, 2023, with questions from the Danish National Well-being Questionnaire (DNWQ) obtained from the Danish agency for IT and Learning (STIL), The ministry of Education (19).

Participants:

Children in the intervention groups were 5 to 10 years of age and participated in one of two different family-centered intervention: a one-year intervention and a three-year intervention. Children with obesity living in one of the municipalities and who were never invited to participate in the interventions will act as a reference group for this study.

Obesity is defined by the International Obesity Task Force (IOTF) guideline as a $BMI \geq 30 \text{ kg/m}^2$ adjusted for age and sex (20). If a child's BMI (adjusted for age and sex) was above this cut-off, the parents were notified, and the family invited to participate in the intervention. After acceptance from the parents, the child was referred to the intervention.

Inclusion criteria:

- Inclusion visit between August 1st, 2014, and June 30th, 2020 (figure 1).
- Obesity at time of referral as defined by the IOTF guideline (20).
- Age between 5 and 10 years at inclusion visit.

- A completed DNWQ within a timeframe of 10 months prior to 2 months after inclusion.
- A completed DNWQ at follow-up (1 to 3 years after inclusion visit).

Exclusion criteria:

- Children declining participation in a community-based lifestyle intervention.

The groups

- Two intervention groups:
 - Children with obesity attending the one-year intervention.
 - Children with obesity attending the three-year intervention.
- Non-intervention group/reference group: children with obesity who were not invited to the interventions.

Outcome:

The outcome of the study will be the children's answers to specific questions from the DNWQ regarding the psychosocial well-being related to school. The DNWQ is a national questionnaire used to examine how primary school-children perceive their well-being and learning environment in school. For the children in 0th to 3rd grade, the questionnaire consists of 20 questions where the children express their level of agreement with each question using a three-point Likert scale, ranging from 1 to 3. For children and adolescents in 4th to 9th grade, the questionnaire consists of 40 questions where the level of agreement with each question is rated on a five-point Likert scale, ranging from 1 to 5. The DNWQ is completed annually from January 20th to March 20th and is an integrated part of the teaching for all school children in public primary schools, including special schools and treatment centers. The DNWQ was introduced in 2015.

We selected four primary and three secondary questions as representative of psychosocial well-being. Our focus will be on the four primary questions. The answers at time of inclusion and follow-up will be included in the analyses. At follow-up the answers of the questionnaire completed closest to two years from the time of inclusion, will be prioritized.

All the questions will be dichotomized into: High well-being / Low well-being. Responses 1 and 2 for grades 0-3 and response 1-3 for grades 4-9 will be characterized as low well-being.

Primary outcomes:

The following four questions have been selected as our primary outcomes

1. Question:

Are you happy with your school?

2. Questions:

Do you feel lonely at school? (0-3 grade)

Do you feel lonely? (4-9 grade)

3. Question:

Is anyone teasing you so that you feel sad? (0-3 grade)

Have you been bullied this school year? (4-9 grade)

4. Question:

Does your stomach ache when you are at school? (0-3 grade)

How often does your stomach ache? (4-9 grade)

Secondary outcomes:

The following three questions has been selected as our secondary outcome

A. Question:

Are you good at solving your problems? (0-3 grade)

How often can you find a solution to problems, just by trying hard enough? (4-9 grade)

B. Question:

Can you concentrate during class?

C. Question:

Are you good at helping each other in class? (0-3 grade)

Most students in my class are friendly and helpful. (4-9 grade)

Data sources and study variables:

Data sources:

1. Children who participated in one of the two interventions will be identified by using data from TM-Sund and NOVAX. Data recorded at obligatory health check-ups at the school containing height and weight can also be extracted from TM-Sund and NOVAX. TM-Sund and NOVAX are data capturing tools used by the community health care nurses employed at the two municipalities, respectively. The reference group will be identified in TM-Sund.
2. The DNWQ data will be obtained from the Danish agency for IT and Learning (STIL), The ministry of Education (19).

3. Data on socioeconomic status (SES), immigration, family structure, and psychiatric diagnoses will be obtained from the national Danish registries through Statistics Denmark (21-23).

We wish to include the following co-variables:

- Inclusion outcome (High well-being / Low well-being)
- Age at inclusion (e.g. 5.8 years)
- BMI z-score (24).
- Sex (girl/boy)
- Highest completed Household Education (HHE)
 - “Short”: Primary school (UNESCO’s International Standard Classification of Education (ISCED) level 1-2).
 - “Middle”: Highschool, vocational education, and similar shorter education (ISCED level 3-5).
 - “Long”: Tertiary education at bachelor level or higher (ISCED level 6-8)
- Immigration status (Danish origin / Immigrants)
- Disposition for mental illness (lifetime) (yes / no)
- Mental illness, child (lifetime) (yes / no)
- Family structure (single caretakers / non-single caretaker)

Statistics:

All statistical analyses will be performed using Stata/SE 15 (StataCorp LP, College Station, Texas, USA).

All statistical tests will be two-sided with a significance level of 0.05.

For the characteristics at time of inclusion:

- Normally distributed data will be analyzed using a one-way ANOVA (several means) and a t-test (two means).
- Non-normally distributed data will be compared using a Kruskal-Wallis test (>2 groups) and a Mann-Whitney U test (2 groups).
- Categorical variables will be analyzed using a Fisher’s exact test.

For missing data (education, immigration status, and family-type), a multiple imputation (MI) with chained equations will be utilized to replace missing values with imputed values. Rubin’s rule will be applied to obtain overall estimates of 100 imputed datasets.

We will perform the analyses in several steps:

Firstly, the McNemar test will be used to investigate potential change in psychosocial well-being from time of inclusion to follow-up for each of the dichotomized Questions 1-4 (primary outcome) and Questions A-C (secondary outcomes) in both intervention groups. All questions will be dichotomized into: high well-being/low well-being.

Secondly, a crude and an adjusted logistic regression analysis will be conducted to compare the change in psychosocial well-being between children in the intervention group and the non-intervention group and between the two intervention groups.

The multivariable model will be adjusted for no more than 1 co-variate per 10 observations of the least common outcome.

The co-variates are listed in prioritized order: 1) Inclusion outcome, 2) BMI z-score, 3) age at inclusion 4) sex, 5) highest completed household education, 6) immigration status, 7) disposition for mental illness, 8) mental illness, and 9) family structure.

As an explorative outcome, a logistic regression model adjusted for change in BMI z-score (from inclusion to follow-up) will be performed to remove the potential effect of weight change on the association between exposure and change in psychosocial well-being based on the primary outcomes (Questions 1-4). The BMI z-score observed closest to the included DNWQ at follow-up will be used.

We wish to investigate the stratified effect of BMI z-score, parental level of education, immigration status and disposition for mental illness before we examine their potential for effect modification for the change in psychosocial well-being for each of the primary questions. These analyses will be conducted across comparisons of each intervention group with the non-intervention group and between the two intervention groups.

Figure 1: Lexi diagram for time of inclusion (x-axis), inclusion age of the participants (y-axis), and time points for the DNWQ.

[figure not shown]

Table 1: Characteristics at time of inclusion, divided by groups:

	One- year Intervention (n =)	Three-year Intervention (n =)	Non- Intervention (n =)
Age (year) at inclusion			
Sex, n (%)			
Boys			
Girls			
BMI z-score			
Highest completed household education, n (%)			
Short			
Middle			
Long			
Family type, n (%)			
Single caretaker			
Non-single caretaker			
Immigration status, n (%)			
Danish origin			
Immigrants			
Parental mental illness (yes), n (%)			
Psychiatric diagnosis, child (yes), n (%)			

Table 2: The distribution of answers to each of the questions on psychosocial well-being at inclusion and follow-up, divided by groups.

n (%)	One-year intervention		Three-year intervention		Non-intervention	
	Inclusion	Follow-up	Inclusion	Follow-up	Inclusion	Follow-up
Question 1: Are you happy with your school?						
High well-being (yes)						
Low well-being (no)						
Question 2: Do you feel lonely at school? (0-3 grade) Do you feel lonely? (4-9 grade)						
High well-being (no)						
Low well-being (yes)						
Question 3: Is anyone teasing you so that you feel sad? (0-3 grade) Have you been bullied this school year? ? (4-9 grade)						
High well-being (no)						
Low well-being (yes)						
Question 4: Does your stomach ache when you are at school? (0-3 grade) How often does your stomach ache? (4-9 grade)						
High well-being (no/rarely)						
Low well-being (yes/often)						
Question A: Are you good at solving your problems? (0-3 grade) How often can you find a solution to problems, just by trying hard enough? (4-9 grade)						
High well-being (yes/often)						
Low well-being (no/rarely)						
Question B: Can you concentrate during class?						
High well-being (yes)						
Low well-being (no)						
Question C: Are you good at helping each other in class? (0-3 grade) Most students in my class are friendly and helpful? (4-9 grade)						
High well-being (yes)						
Low well-being (no)						

Table 3: McNemar's test and logistic regression analyses for the primary outcomes comparing the change in psychosocial well-being between intervention and non-intervention group:

	Question 1	Question 2	Question 3	Question 4
	OR (95% CI), p- value	OR (95% CI), p- value	OR (95% CI), p- value	OR (95% CI), p- value
McNemar's				
One-year intervention				
Three-year intervention				
Logistic regression model 1 ^a				
One-year vs Non-intervention				
Three-year vs Non-intervention				
Three-year vs. one-year intervention				
Logistic regression model 2 ^b				
One-year vs Non-intervention				
Three-year vs Non-intervention				
Three-year vs. one-year intervention				

^aLogistic regression model with the groups as the independent variable, the follow-up outcome as the dependent variable, and adjusted for the co-variable: inclusion outcome.

^bLogistic regression model with the groups as the independent variable, the follow-up outcome as the dependent variable, and the following covariates: inclusion outcome, age, BMI z-score, sex, highest completed household education, immigration status, disposition for mental illness, mental illness (child), and family structure.

OR: odds ratio; CI: confidence interval.

Table 4: McNemar's test and logistic regression analyses for the secondary outcomes comparing the change in psychosocial well-being between intervention and non-intervention group:

	Question A	Question B	Question C
	OR (95% CI), p-value	OR (95% CI), p-value	OR (95% CI), p-value
McNemar's			
One-year intervention			
Three-year intervention			
Logistic regression model 1 ^a			
One-year vs Non-intervention			
Three-year vs Non-intervention			
Three-year vs. one-year intervention			
Logistic regression model 2 ^b			
One-year vs Non-intervention			
Three-year vs Non-intervention			
Three-year vs. one-year intervention			

^aLogistic regression model with the groups as the independent variable, the follow-up outcome as the dependent variable, and adjusted for the co-variable: inclusion outcome.

^bLogistic regression model with the groups as the independent variable, the follow-up outcome as the dependent variable, and the following covariates: inclusion outcome, age, BMI z-score, sex, highest completed household education, immigration status, disposition for mental illness, mental illness (child), and family structure.

OR: odds ratio; CI: confidence interval.

Table 5: Effect modification analyses of the primary outcomes comparing the change in psychosocial well-being between the one-year intervention and non-intervention groups.

Subgroup	Number of children			aOR (95% CI for the primary outcomes)				P-value for interaction
	Total	Non-intervention	One-year intervention	Q1	Q2	Q3	Q4	
BMI z-score								
< 3								
> 3								
Highest completed household education								
Shorter								
Longer								
Parental mental illness								
Yes								
No								
Immigration status								
Danish origin								
Immigrants								
Full population								

The adjusted odds ratios and 95% intervals (CI) for the primary outcome (Q1-4 at follow-up) displayed, comparing the intervention group to the non-intervention group after adjusting for the following co-variables (excluding the one stratified for): inclusion outcome, age, BMI z-score, sex, highest completed household education, immigration status, disposition for mental illness, mental illness (child), and family structure.

OR: odds ratio; CI: confidence interval.

Table 6: Effect modification analyses of the primary outcomes comparing the change in psychosocial well-being between the three-year intervention and non-intervention groups.

Subgroup	Number of children			aOR (95% CI for the primary outcomes)				P-value for interaction
	Total	Non-intervention	Three-year intervention	Q1	Q2	Q3	Q4	
BMI z-score								
< 3								
> 3								
Highest completed household education								
Shorter								
Longer								
Parental mental illness								
Yes								
No								
Immigration status								
Danish origin								
Immigrants								
Full population								

The adjusted odds ratios and 95% intervals (CI) for the primary outcome (Q1-4 at follow-up) displayed, comparing the intervention group to the non-intervention group after adjusting for the following co-variables (excluding the one stratified for): inclusion outcome, age, BMI z-score, sex, highest completed household education, immigration status, disposition for mental illness, mental illness (child), and family structure.

OR: odds ratio; CI: confidence interval.

Table 7: Effect modification analyses of the primary outcomes comparing the change in psychosocial well-being between the three-year intervention and one-year-intervention groups.

Subgroup	Number of children			aOR (95% CI for the primary outcomes)				P-value for interaction
	Total	One-year intervention	Three-year intervention	Q1	Q2	Q3	Q4	
BMI z-score								
< 3								
> 3								
Highest completed household education								
Shorter								
Longer								
Parental mental illness								
Yes								
No								
Immigration status								
Danish origin								
Immigrants								
Full population								

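### Does the single numeric cut for low well-being misclassify the negatively worded questions, given that the plan never says what code 1 means?

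*Combined protocol and SAP*

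**What the plan says.** The Outcome section describes a three-point scale for grades 0-3 (codes 1 to 3) and a five-point scale for grades 4-9 (codes 1 to 5). It calls both measures of agreement. It then gives one rule for every question: "Responses 1 and 2 for grades 0-3 and response 1-3 for grades 4-9 will be characterized as low well-being". No answer labels are attached to the codes, and reverse coding is not mentioned.

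Table 2 gives the direction of each question in words. Yes (or often) is high well-being for Questions 1, A, B and C, and low well-being for Questions 2, 3 and 4. The clearest contrast is between two items that both ask about frequency in grades 4-9. For Question 4 ("How often does your stomach ache? (4-9 grade"), Table 2 has "High well-being (no/rarely"). For Question A ("How often can you find a solution to problems, just by trying hard enough? (4-9 grade"), it has "Low well-being (no/rarely"). Each question has one pair of rows, which covers both grade versions.

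The first analysis step in the Statistics section only restates the split: "All questions will be dichotomized into: high well-being/low well-being". The Data sources section names the holder of the questionnaire data ("The DNWQ data will be obtained from the Danish agency for IT and Learning (STIL") and does not describe the coding.

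**The concern.** A literal reader takes the codes as degrees of agreement running the same way on every question. One cut cannot then serve both the favourably and the unfavourably worded questions. Whichever end is code 1, some questions would have their classes the wrong way round relative to Table 2. Reading the scale as frequency does not help, because Questions 4 and A need opposite directions.

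The stakes would be real if this happened. The dichotomised answer is the McNemar variable, the dependent variable of every logistic model and the first-priority covariate. It also determines the count of the least common outcome, which limits the number of covariates. Because the middle answer is low in either direction, a reversed item would not be a mirror image that could be put right by inverting the odds ratio.

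The two grade versions add a further worry. Children enter at 5 to 10 years and are followed for 1 to 3 years, so some may answer the younger version at inclusion and the older one at follow-up. A difference in code direction between versions would then look like a change in well-being.

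**Working it through.** The plan gives no figure to reproduce on this point. The check sets the numeric rule against the Table 2 labels under each possible meaning of code 1.

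**Inputs.** From the Outcome section: low = codes 1-2 of 3, or codes 1-3 of 5, on all questions. From Table 2: the favourable end is yes/often for Questions 1, A, B and C, and no/rarely for Questions 2, 3 and 4.

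**Step 1: agreement between the rule and Table 2.** The rule makes code 1 low, so it matches Table 2 on a question only if code 1 is the unfavourable end of that question.

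| Meaning of code 1 | Questions in conflict | Of 7 questions | Of 4 primary |
|---|---|---|---|
| Least agreement or frequency, all questions | 2, 3, 4 | 3 | 3 |
| Most agreement or frequency, all questions | 1, A, B, C | 4 | 1 |
| Least favourable answer, question by question | none | 0 | 0 |

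Counting the grade versions separately, and assuming that both run the same way, gives 7 × 2 = 14 item-versions. The conflicts are then 3 × 2 = 6, 4 × 2 = 8, and 0.

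**Step 2: is there a joint reading, and is it unique?** Each question can have code 1 at either end, so there are 2^7 = 128 orientations. Each question matches Table 2 in exactly one of its two directions, so exactly one of the 128 matches throughout: code 1 = least favourable on every question. With the grade versions free to differ there are 2^14 = 16,384 orientations, and again exactly one matches. A rule and a table with one common solution do not contradict each other.

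**Step 3: do the two together classify every answer?** Table 2 names only the ends of each scale and does not place the middle answer. The numeric rule does: code 2 of 3 and code 3 of 5 are low. These are the middle codes in either direction, so their class does not depend on orientation. Table 2 settles the ends and the rule settles the middle. No answer is left without an intended class.

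**Step 4: what a misread item would involve.** On the three-point scale, reversing the order changes the low set from ranks {1, 2} to {2, 3}, so ranks 1 and 3 change class (2 of 3 answers). On the five-point scale it changes from {1, 2, 3} to {3, 4, 5}, so ranks 1, 2, 4 and 5 change (4 of 5). This shows what a coding error would do. It is not evidence that one is planned. The documents give no response distribution, so no effect on a prevalence or odds ratio can be derived.

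**Step 5: how firm is the agreement wording?** The seven questions have 12 distinct wordings: 9 direct questions, 2 on frequency, and 1 statement ("Most students in my class are friendly and helpful. (4-9 grade"). Only that last one is something a child can literally agree with. The reference to agreement comes in a general description of the 20- and 40-question instruments, not in the coding rule. It reads as loose description.

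**The case for a change.** The strongest case for a change is that analysts receive codes, not labels, and that the plan's stated purpose includes describing data management. The recoding of the primary outcome belongs there. As written, the rule cannot be programmed from the text alone with certainty that it reproduces Table 2, and the agreement wording points away from the one coding that works. The remedy would cost a sentence.

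Part of this stands. The code direction is not stated for either grade version, and the wording is imprecise. It does not follow that the outcome is inconsistently defined. Using a codebook to link codes to answers is normal for externally held data. It is also unavoidable here: the rows of Table 2 carry answer labels, so whoever fills them must find out which code is which answer. That same step would reveal an item, or a grade version, whose codes run the other way, because each question has a single pair of labelled rows for both versions.

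Making Table 2 the sole definition would not be an improvement, since it does not place the middle answer. The numeric cut would still be needed, and the resulting classes would be those already intended.

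**Conclusion.** No change to the plan follows. This is a missing detail with loose wording, not a contradiction in the primary outcome. The cut and Table 2 agree on 7 of 7 questions when code 1 is the least favourable answer. That is the only orientation in which they agree, and read together they give the intended class of every answer. The conflicts on 3 or 4 of 7 questions arise only under a common agreement or frequency direction, which the plan never adopts as a coding rule.

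The conclusion rests on two assumptions: that Table 2 expresses the authors' intent, and that the analyst reads the data holder's codebook before dichotomising. The actual code direction cannot be checked from the documents. If some supplied codes ran the other way, the intended classes would be unchanged and those items would simply be recoded to match. Writing the mapping out would record what a competent analyst does anyway, without altering the cut, the classes or any planned analysis.

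### The never-invited reference comes from one municipality and participants from both, with municipality in no model: show programme by municipality, add a within-municipality contrast where one exists, and label the rest

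*Combined protocol and SAP*

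**What the plan says.** Under Data sources, the SAP states: "Children who participated in one of the two interventions will be identified by using data from TM-Sund and NOVAX". It describes the two systems as follows: "TM-Sund and NOVAX are data capturing tools used by the community health care nurses employed at the two municipalities, respectively". The record system therefore identifies the municipality. For the comparison group, the text is: "The reference group will be identified in TM-Sund".

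Under Participants, the reference is defined as "Children with obesity living in one of the municipalities and who were never invited to participate in the interventions". Read alone, that could mean either municipality, but the Data sources sentence settles it as the TM-Sund one.

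The same section gives the invitation rule: if a child's BMI "was above this cut-off, the parents were notified, and the family invited to participate in the intervention".

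The Statistics section lists nine covariates in priority order, from inclusion outcome to family structure. It allows at most one covariate per 10 observations of the rarer outcome. By the footnotes to Tables 3 and 4, model 1 adjusts for the inclusion outcome only and model 2 for all nine. Municipality is not among the nine. It is also absent from Table 1, from the exploratory model adjusted for change in BMI z-score, and from the effect-modification Tables 5 to 7. No restriction or sensitivity analysis by municipality is planned.

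**The concern.** The outcomes are answers about life at school: liking school, loneliness, teasing or bullying, and stomach ache. Children in different municipalities will generally attend different schools, so local school conditions could plausibly shift these answers whether or not a child joined a programme. Adjusting for the inclusion answer removes only part of a stable difference, and individual covariates need not capture local conditions.

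As planned, a municipality difference would enter the reported odds ratio wherever NOVAX participants are set against the TM-Sund reference, and no table would let a reader see it. The odds ratios against the reference are the plan's main evidence on whether a programme did anything beyond what would have happened anyway. The McNemar tests compare each child with itself and are not affected.

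**Working it through.** The SAP gives no sample size, prevalence or effect size, so there is no planned figure to reproduce. The first two steps are structural. The last two are illustrations.

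**1. Which contrasts cross municipalities.** The documents do not give the allocation of programmes, so each possibility that has participants in both systems is listed.

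| Allocation | Contrasts with the reference | Three-year vs one-year |
|---|---|---|
| One programme per municipality | One wholly cross-municipality; the other already within TM-Sund | Wholly cross-municipality |
| One programme in both, the other in TM-Sund only | One partly affected | Depends on the mix |
| One programme in both, the other in NOVAX only | One partly, one wholly affected | Depends on the mix |
| Both programmes in both | Both partly affected | Depends on the mix |

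At least one of the two reference contrasts is affected in every row. Table 5 or Table 6 follows the matching contrast.

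**2. Whether a municipality covariate would solve it.** Take the pairwise model with columns (intercept, programme, NOVAX).
- Programme only in NOVAX: the distinct rows are (1,0,0) for the reference and (1,1,1) for participants. The rank is 2 of 3, so programme and municipality are aliased and cannot be separated.
- Programme in both: the rows are (1,0,0), (1,1,0) and (1,1,1). The rank is 3 of 3, so both terms can be estimated. The municipality effect then comes from participants only and must be assumed equal in the reference.
- Three-year vs one-year with each programme in a different municipality: again rank 2 of 3.

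**3. Illustrative size under model 1.** All inputs are assumed:
- no programme effect;
- 30% low well-being in the TM-Sund municipality;
- the NOVAX municipality 5 or 10 percentage points away, at both times;
- latent normal within-child correlation r of 0.3, 0.5 or 0.7;
- equal group sizes.

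Expected cell proportions were fitted by logistic regression of follow-up low well-being on group and inclusion outcome.

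One case in full: 30% versus 20%, r = 0.5, all participants in NOVAX. The cells (low-low, low-high, high-low, high-high, inclusion then follow-up) are 0.1568, 0.1432, 0.1432, 0.5568 in the reference and 0.0872, 0.1128, 0.1128, 0.6872 in participants.
- Low at inclusion: OR = (0.0872/0.1128)/(0.1568/0.1432) = 0.71.
- High at inclusion: OR = (0.1128/0.6872)/(0.1432/0.5568) = 0.64.
- The fitted common OR is 0.66. The unadjusted OR is (0.20/0.80)/(0.30/0.70) = 0.58, so model 1 removes part of the difference but not all of it.

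| NOVAX minus TM-Sund, low well-being | All participants in NOVAX | Half in NOVAX |
|---|---|---|
| -10 points | 0.63 to 0.69 | 0.81 to 0.84 |
| -5 points | 0.81 to 0.84 | 0.90 to 0.92 |
| +5 points | 1.17 to 1.21 | 1.08 to 1.10 |
| +10 points | 1.35 to 1.45 | 1.17 to 1.21 |

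Ranges run over the three values of r. The half-NOVAX column applies only if a programme ran in both municipalities.

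**4. Precision cost of restricting to TM-Sund.** With f the share of a programme's participants in TM-Sund and k the ratio of reference to participants, the standard error of the log odds ratio rises by about sqrt((1/f + 1/k)/(1 + 1/k)). For f = 0.5 and k = 1 this is sqrt(3/2) = 1.22. Over f from 0.25 to 0.75 and k from 0.5 to 2 it runs from 1.05 to 1.73. These values are also assumed.

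**The case against.** The strongest reply is that a TM-Sund-only contrast may add nothing. Two programmes, two systems and two municipalities suggest that each municipality may have run one programme. The TM-Sund programme's planned contrast would then already be within one municipality, and the NOVAX programme would have no such contrast. This stands, so the extra contrast has to be conditional on a programme having run in both. In the one-programme-per-municipality case, what remains is disclosure and labelling, which the plan does not provide for.

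It also stands that model 2 may absorb part of a municipality difference through education, immigration status, family structure and the other covariates. No figure for model 2 can be offered. The cost is not trivial either. Two programmes, two models and seven questions make up to 2 x 2 x 7 = 28 extra estimates, and a smaller sample may lose covariates under the one-per-10 cap.

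Some stronger readings are tempting but not supported:
- A reader might infer that both reference contrasts are biased, or biased in the programmes' favour. With one programme per municipality only one of the two is affected, and nothing in the documents gives a direction.
- A reader might infer that the restricted contrast is free of selection. It is not, because the reason the reference children were not invited is not given.
- A reader might add that the reference has no index date. Figure 1 is not shown in the available text, so that cannot be held against the plan.
- Participants are acceptors, since "After acceptance from the parents, the child was referred to the intervention", and decliners are excluded. That is a limitation to expect in a declared observational cohort. Its effect cannot be sized from the documents, and nothing shows that data on decliners exist for a further analysis.

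**Conclusion.** The point holds in a limited form, as a cheap improvement. The text establishes that the reference is from one municipality, that participants come from both systems, and that no model or table carries municipality. It follows that at least one reference contrast compares children across municipalities without saying so, and that a municipality difference would be reported as a programme effect there.

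Which contrasts are affected depends on an allocation that the documents do not state. Whether a difference exists, how large it is and which way it points cannot be derived from them. The odds ratios above show only that, under model 1, a gap of 5 to 10 points could give values from 0.63 to 1.45 with no programme effect. They rest wholly on the assumed prevalence, gap and correlation.

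**What to change.** Amend the Statistics section and the table shells before analysis:

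1. Report the number of children by programme and municipality, for example in Table 1.
2. For any programme with participants in both municipalities, add a contrast of TM-Sund participants with the TM-Sund reference, under models 1 and 2. Do this for the four primary questions in Table 3, and for Table 4 where numbers allow. Use the covariate set of the main model where the one-per-10 cap permits, and state any covariate dropped.
3. For any programme with no TM-Sund participants, label its contrast with the reference as cross-municipality, in Tables 3 and 4 and in the matching Table 5 or 6, and do not attribute it to the programme alone. Do the same for three-year versus one-year (Tables 3, 4 and 7) if each programme ran in a different municipality. Adding a municipality covariate does not help in these cases, because it is aliased with group.
4. State why the reference children were not invited, given the invitation rule under Participants, and note that the restricted contrast does not remove any selection this caused.

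No new data are needed, because the source system already identifies the municipality. The planned contrasts stay in place. The added rows number at most 2 x 2 x 4 = 16 estimates in Table 3, or 28 with Table 4. The restricted estimates will be less precise (about 1.22-fold in standard error in the equal-size, half-in-TM-Sund case) and may carry fewer covariates.
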